**Table 4. Dose Modification and Re-treatment Criteria for Oral and IV Study Drugs**

| Adverse Event   | Severity (CTCAE Grade) | Oral Study Drug (rucaparib)                               |                                    | IV Study Drug (nivolumab)      |                                    |
|---|------------------------|---|------------------------------------|--------------------------------|------------------------------------|
|   |                        | Dose Modification                             | Re-treatment                       | Dose Modification  | Re-treatment                       |
| Endocrinopathy AEs    | 3                      |   |                                    | Hold                           | Grade ≤ 1 or baseline  |
| Non-hematological Toxicity (Skin)  |                        |   |                                    |                                |                                    |
| Adverse event   | 3                      | Hold  | Grade 2                | Hold                           |                                    |
| Hematological Toxicity   |                        |   |                                    |                                |                                    |
| Hematological toxicity (related events lasting >7 days for nivolumab, exceptions below) | 3-4                    | Hold    | Grade 2                | Discontinue                    |                                    |
| Confirmed MDS or AML (all new secondary malignancies are Grade 4 per CTCAE 5.0)         | 4                      | Discontinue   |                                    | Discontinue                    |                                    |
| Exceptions with nivolumab  |                        |   |                                    |                                |                                    |
| Laboratory abnormalities except as specified below                                      | 3                      |   |                                    | Hold                           | Grade ≤ 1 or baseline  |
| Thrombocytopenia > 7 days or associated with bleeding                                   | 3                      |   |                                    | Discontinue                    |                                    |
| Laboratory abnormality except for those below that do not require delay                 | 4                      |   |                                    | Discontinue                    |                                    |
| Neutropenia ≤ 7 days  | 4                      |   |                                    | Hold                           | Grade ≤ 1 or baseline  |
| Lymphopenia or leukopenia   | 4                      |   |                                    | Hold                           | Grade ≤ 1 or baseline  |
| Laboratory Abnormalities   |                        |   |                                    |                                |                                    |
| Laboratory abnormality  | 3                      | Hold  | Grade 2                | Hold                           |                                    |
| ALT, AST, and/or bilirubin abnormalities  | 2                      | None  | N/A                                | Hold               | Grade ≤ 1 or baseline  |
| ALT/AST elevations  | 3                      | None, provided no signs of liver dysfunction  | N/A                                | Discontinue        |                                    |
| ALT/AST elevations  | 4                      | Hold  | ≤Grade 2 Reduce dose  | Discontinue                    |                                    |

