| Endocrinopathies, adequately controlled with only physiologic hormone replacement  | 3                      |                                |                        | Hold                           | Grade ≤ 1 or baseline  |
| Drug-related adrenal insufficiency or hypophysitis   | 2                      |                                |                        | Hold                           | Grade ≤ 1 or baseline  |
| Adrenal insufficiency regardless of control with hormone replacement   | 3                      |                                |                        | Discontinue                    |                                    |
| Laboratory abnormalities except as specified below   | 3                      |                                |                        | Hold                           | Grade ≤ 1 or baseline  |
| Drug-related ALT, AST, or bilirubin  | 3                      |                                |                        | Discontinue        |                                    |
| Adverse event or laboratory abnormality except for those below that do not require delay   | 4                      |                                |                        | Discontinue                    |                                    |
|  |                        |                                |                        |                                |                                    |
| Isolated electrolyte imbalances/abnormalities not associated with clinical sequelae/corrected w/supplementation /appropriate management w/in 72 hours of onset | 3               |                                |                        | Hold                           | Grade ≤ 1 or baseline  |

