Patients may resume treatment with IV study drug when the drug-related AE(s) improve to Grade ≤ 1 or resolve to baseline value, with the following exceptions which are allowed: Grade 2 fatigue, Grade 2 skin toxicity (if no Grade 3 drug related skin AE). For patients with Grade 2 AST, ALT, or total bilirubin elevations, dosing may resume when laboratory values return to baseline and management with corticosteroids, if needed, is complete. Drug-related pulmonary toxicity, diarrhea or colitis must have resolved to baseline before treatment is resumed. Patients with persistent Grade 1 pneumonitis after completion of a steroid taper over at least 1 month may be eligible for retreatment if discussed with and approved by the study medical monitor. Patients with drug-related endocrinopathies adequately controlled with only physiologic hormone replacement may resume treatment after consultation with the study medical monitor. Adrenal insufficiency requires discontinuation regardless of control with hormone replacement.

The patient may continue at same or reduced dose at the discretion of the investigator. If treatment is resumed at the same dose, and the patient experiences the same toxicity, treatment should be interrupted, then resumed at a reduced dose following improvement of the event to ≤ CTCAE Grade 2. If the patient continues to experience toxicity, additional dose reduction steps are permitted; however, the investigator should consult with the sponsor's medical monitor before reducing to 300 mg BID.

In most cases of Grade 3 ALT or AST elevation, IV study drug will be permanently discontinued. For patients with Grade 3 ALT or AST elevations after the start of IV dosing, but on a background of previous elevations on the first cycle of oral study drug, IV study drug hold is required, but discontinuation is not required, if ALT/AST elevations begin to resolve before the next scheduled infusion, and toxicity is considered to be mainly related to oral study treatment, after the investigator discusses the case with the study medical monitor. Levels will be monitored every 3 days; if they continue to rise more than 20%, the Hepatic Adverse Event Management Algorithm for a Grade 3 event will be followed. Treatment with IV drug may be resumed if levels return to Grade 2. If total bilirubin elevations > 2 × ULN accompany any of the ALT/AST elevations, IV drug should be discontinued.

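### After a Grade 2 liver-test event, the Table 4 nivolumab restart cell and its own footnote 3 give opposite answers for a value at Grade 1 but above baseline.

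*Combined protocol and SAP*

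**What the plan says.** All of this is in Section 6, Table 4 and its footnotes.

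- **Grade 2 row.** Under Laboratory Abnormalities, the row "ALT, AST, and/or bilirubin abnormalities" leaves rucaparib unchanged and holds nivolumab (footnote 8). The nivolumab re-treatment cell reads "Grade ≤ 1 or baseline" and carries footnote 3.
- **Footnote 3, general sentence.** "Patients may resume treatment with IV study drug when the drug-related AE(s) improve to Grade ≤ 1 or resolve to baseline value", followed by permitted exceptions for Grade 2 fatigue and Grade 2 skin toxicity.
- **Footnote 3, liver sentence.** "For patients with Grade 2 AST, ALT, or total bilirubin elevations, dosing may resume when laboratory values return to baseline", and any corticosteroid management must also be complete.
- **Footnote 5.** "In most cases of Grade 3 ALT or AST elevation, IV study drug will be permanently discontinued". For a defined subset a hold replaces discontinuation, and then "Treatment with IV drug may be resumed if levels return to Grade 2".
- **Footnote 8.** The Grade 2 hold is waived for ALT/AST rises that start after oral dosing, are resolving before the next infusion and are attributed mainly to rucaparib.
- **Pointers at Grade 3.** The row "Drug-related ALT, AST, or bilirubin" under the nivolumab exceptions points to footnote 5. The Grade 3 ALT/AST row under Laboratory Abnormalities points to footnote 7, which is about persistent blood-count abnormalities and referral to a hematologist.

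Table 4 also requires nivolumab to be discontinued when a delay exceeds 8 weeks from the previous dose. Prolonged steroid tapers are exempt, and non-drug-related delays may be approved.

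**The concern.** The restart level decides whether a held patient receives the next infusion, and two texts in the same cell set it differently. Sites will meet the rule. Section 2.3.4 lists ALT/AST increases among the most common rucaparib events, including at Grade 3 or higher. Table 4 continues rucaparib through Grade 2, and the Study Calendar adds a Cycle 1 Day 15 liver check.

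Under one reading, nivolumab is given at a value that the other reading treats as not yet recovered. Under the other, the patient stays held and may reach the delay limit, which ends nivolumab. Two patients with the same result could be managed differently, and the toxicity profile (objective 1.2.4) would describe a regimen delivered under two rules. Section 11.2 plans no separate analysis of nivolumab exposure or discontinuation, so the stake is patient management and consistent delivery rather than a planned estimate.

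**Working it through.** The plan states no figure to reproduce. The check sets the rules side by side and then follows the timing.

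**1. Grade 2 event with the hold in force**

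| Current value | Cell | Footnote 3, liver sentence |
|---|---|---|
| At baseline | Restart | Restart once any steroid management is complete |
| Grade 1, above baseline | Restart | Stay held |
| Still Grade 2, above baseline | Stay held | Stay held |

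The middle line is a direct conflict for ALT, AST and bilirubin. On the first line the texts agree on the level, but the cell does not state the steroid condition.

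**2. Width of the gap for ALT/AST**

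The documents print no grade cut-offs. Assume grading in multiples of ULN with Grade 1 ending at 3 x ULN. Let b be the baseline in multiples of ULN.

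- Highest restart value under the cell: max(3, b).
- Highest restart value under footnote 3: b.
- Gap: max(3, b) − b.

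| b | Cell | Footnote 3 | Gap |
|---|---|---|---|
| 1 | 3 | 1 | 2 |
| 2 | 3 | 2 | 1 |
| 3 (eligibility limit, 3.1.5) | 3 | 3 | 0 |
| 5 (limit with liver metastases) | 5 | 5 | 0 |

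Example with b = 1: ALT falls from 4 to 2 x ULN. Since 2 ≤ 3, the cell permits restart. Since 2 > 1, footnote 3 keeps the hold. If grades were instead counted relative to an abnormal baseline, a Grade 1 band above baseline would remain for those patients too.

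**3. Timing**

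Nivolumab is given every 4 weeks (5.2), and footnote 2 restarts a held patient in the next scheduled window.

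- Last dose: week 0.
- Dose held: week 4.
- Next slot: 2 × 4 = week 8, which is at the limit.
- If still held, following slot: 3 × 4 = week 12, and 12 > 8.

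For a patient at Grade 1 above baseline at week 8, the cell leads to an infusion. Footnote 3 leads to a further hold and, unless an exemption applies, discontinuation.

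**4. Grade 3 ALT/AST**

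Footnote 5 permits restart at Grade 2 only where all of these hold: earlier elevations on the first cycle of oral drug, values resolving before the next infusion, attribution mainly to rucaparib, and discussion with the medical monitor. Bilirubin above 2 x ULN alongside the ALT/AST rise removes the option.

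Once such a value falls to Grade 2, the Grade 2 row would call for a hold. Footnote 8 waives that hold on two of the same conditions (resolving, mainly due to rucaparib), so the two footnotes can be read together. However, footnote 8 addresses Grade 2 elevations and says when a hold is unnecessary, whereas footnote 5 starts from a hold already required. Neither refers to the other. A reader who starts from the Grade 3 ALT/AST row under Laboratory Abnormalities is sent to footnote 7 and is not led to footnote 5.

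**The case against.** The strongest reply is that the cell is a stock phrase repeated across many rows, and that footnote 3 supplies event-specific qualifications, so the specific text governs. This is a plausible reading. It works well for the general Grade 2 adverse-event row, where the phrase covers many events and the footnote tightens a few. It works less well here, because the row is already confined to Grade 2 ALT, AST and bilirubin, exactly the events in the footnote sentence. If the footnote governs, the Grade 1 alternative has no function in that row. If the footnote sentence is read as merely permissive, its restart level adds nothing to the cell. Either way some of the text is idle, and the document does not say which.

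The reply also limits the impact, and much of this stands. Many resolving ALT/AST rises attributed to rucaparib fall under footnote 8 and never reach a restart decision. The delay rule exempts prolonged steroid tapers, and Section 7.1.1 calls for steroids in Grade 2 immune-mediated hepatitis. The patients at risk of discontinuation are therefore those whose hold was not waived and who have no prolonged taper at week 8. Footnote 8 covers ALT and AST only, so isolated bilirubin rises remain exposed.

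A reader might also infer that Table 4 sets three competing restart levels for one liver result, with the loosest following the most severe event. The documents do not support that:

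- The Grade 2 level comes only from footnote 5, for a conditional subset of Grade 3 ALT/AST events; most Grade 3 cases are discontinued.
- Bilirubin has two levels, not three.
- Grade 4 ALT/AST and suspected drug-induced liver injury are discontinued with no restart.
- Outside the footnote 5 subset, a fall from Grade 3 to Grade 2 does not permit restart; within it, footnote 8 can remove the apparent clash with the Grade 2 hold.

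**Conclusion.** The point holds in a narrow form. For a Grade 2 ALT, AST or bilirubin event, the re-treatment cell and its attached footnote give opposite instructions at one level: Grade 1 but above baseline. That conflict rests on the wording alone and needs no assumed cut-off.

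Its width does depend on assumptions. With Grade 1 taken to end at 3 x ULN, the ALT/AST gap ranges from 2 x ULN (baseline 1 x ULN) to nothing (baseline 3 x ULN or higher). At its most consequential, it separates an infusion at week 8 from discontinuation under the delay limit, subject to the exemptions. The documents give no rate of Grade 2 liver events for the combination, so the number of the 36 planned patients affected cannot be stated.

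The unstated interaction of footnotes 5 and 8, and the differing footnote pointers at Grade 3, are secondary gaps in clarity. They are not further contradictions of the same kind. No view is taken on which restart level is right. The correction should be made because this is an operative safety rule.

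**What to change.** 1. Reconcile the Grade 2 ALT/AST/bilirubin re-treatment cell with footnote 3 so that one nivolumab restart level applies, and make clear whether completion of corticosteroid management is part of it. The sponsor's clinical team chooses the level.
2. State how footnotes 5 and 8 interact once a Grade 3 ALT/AST value has fallen to Grade 2.
3. Reconcile the footnote pointers on the two Grade 3 liver rows (footnote 5 on one, footnote 7 on the other).

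The cost is a wording amendment to one table cell, the footnotes concerned and the row pointers, with the usual committee and IRB review under Section 4.1. It needs no extra tests, visits or patients.

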Such as, hyper- or hypothyroidism, or glucose intolerance, that resolve or are adequately controlled with physiologic hormone replacement (corticosteroids, thyroid hormones) or glucose-controlling agents, respectively, may not require discontinuation after discussion with and approval from the study medical monitor/designee. Grade 4 drug-related adrenal insufficiency or hypophysitis requires discontinuation regardless of control with hormone replacement.

If any blood parameters remain clinically abnormal > 4 weeks of dose interruption, the patient should be referred to hematologist for further investigations. Bone marrow analysis and/or blood cytogenetic analysis should be considered at this stage according to standard hematological practice.

For patients with Grade 2 ALT or AST elevations with onset after dosing of oral study drug, IV study treatment hold is not required if ALT/AST elevations begin to resolve before the next scheduled infusion and toxicity is considered to be mainly related to oral study treatment. If a subsequent ALT/AST increase of more than 20% is observed following infusion of IV study drug, the next IV study drug administration will be held and, if further increase is observed, the Hepatic Adverse Event Management Algorithm will be followed. In this case, IV study drug should be discontinued if Grade 2 elevations return post re-challenge. If total bilirubin elevations > 2 × ULN accompany any of the ALT/AST elevations, IV drug should be discontinued.

Bilirubin must be within normal limits and alkaline phosphatase must be < 3 x ULN. Monitor liver function tests weekly. If the patient has Grade 3 ALT/AST and continues on oral study drug, and levels do not decline within 2 weeks or they continue to rise, treatment interruption and improvement to ≤ Grade 2 will be required before oral study drug can be resumed, either at the current dose or at a reduced dose.

Monitor liver function tests weekly for 3 weeks after oral study drug has been restarted.

Grade 2 for nivolumab is described as ≥ 1.5 x baseline and baseline is the day the combination treatment starts (ie, Cycle 2 Day 1 in Cohort A1 and A2, and Cycle 1 Day 1 in Cohort B)

| RECOMMENDED DOSE ADJUSTMENTS FOR RUCAPARIB |   |                         |
|--|---|-------------------------|
|  | Dose   | Total mg per day |

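### Table 4 gives two different nivolumab rules for Grade 3 ALT/AST elevation in patients who meet the footnote 5 conditions, because one of its two rows cites a hematology footnote instead

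*Combined protocol and SAP*

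**What the plan says.** Section 6 states that dose modification and re-treatment of both study drugs follow Table 4. Two specific rows of that table cover Grade 3 ALT/AST.

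- **Non-hematological AEs, exceptions with nivolumab.** The event is "Drug-related ALT, AST, or bilirubin", Grade 3, and the nivolumab entry is "Discontinue 5" (the number is the footnote marker).
- **Laboratory abnormalities.** The event is ALT/AST elevation, Grade 3, with no restriction to drug-related events. The rucaparib entry is "None, provided no signs of liver dysfunction", with footnote 9. The nivolumab entry is "Discontinue 7", and the nivolumab re-treatment cell is empty.

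Footnote 5 begins: "In most cases of Grade 3 ALT or AST elevation, IV study drug will be permanently discontinued". It then describes a patient whose rise comes after the start of IV dosing, on a background of elevations in the first cycle of oral drug. For that patient, "IV study drug hold is required, but discontinuation is not required, if ALT/AST elevations begin to resolve before the next scheduled infusion", provided also that the toxicity is judged mainly due to the oral drug and that the investigator has discussed the case with the medical monitor. Nivolumab may restart at Grade 2. Total bilirubin above 2 x ULN takes the exception away.

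Footnote 7 reads: "If any blood parameters remain clinically abnormal > 4 weeks of dose interruption, the patient should be referred to hematologist". It goes on to bone marrow and cytogenetic work-up and says nothing about ALT, AST or nivolumab.

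**The concern.** A patient with drug-related Grade 3 ALT/AST who satisfies footnote 5 falls under both rows. One row gives a hold with a route back to nivolumab. The other, as printed, gives discontinuation with no exception, because its marker leads to a note on another subject.

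The situation is foreseeable. Section 2.3.4 lists raised ALT/AST among the most common rucaparib events of Grade 3 or higher, and the study calendar adds a Cycle 1 Day 15 panel to assess liver function. What is at stake is whether a patient permanently loses one of the two drugs under test according to which row the investigator reads. Uneven application would also affect nivolumab exposure and the count of discontinuations for toxicity, which belong to the toxicity objective in Section 1.2.4.

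**Working it through.** The plan gives no figure to reproduce, so the main check sets the two rows side by side.

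| | Drug-related row | Laboratory row |
|---|---|---|
| Event | ALT, AST or bilirubin, Grade 3 | ALT/AST, Grade 3 |
| Relatedness limit | Yes | None |
| Nivolumab entry | Discontinue | Discontinue |
| Footnote cited | 5 | 7 |
| Subject of footnote | Grade 3 ALT/AST; conditional hold | Persistent blood abnormalities; hematology referral |
| Route to resume nivolumab | Yes, at Grade 2 | None |

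**Where the rows overlap.** Both apply to drug-related Grade 3 ALT/AST. Within that group they give the same result unless all of these hold: earlier elevations on the first cycle of oral drug; values beginning to resolve before the next infusion; toxicity mainly related to the oral drug; discussion with the medical monitor; and total bilirubin not above 2 x ULN. Only then does one row print a hold and the other discontinuation.

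**Whether marker 7 could be a text-reading error.** Markers 8, 9 and 10 in the neighboring liver cells all lead to liver footnotes. Marker 7 also stands on the rucaparib hold for hematological toxicity, where its content fits. An extraction error is therefore not evident. Footnote 11 refers to Cohorts A1, A2 and B, which this single-arm trial does not have, so the footnotes do not appear to have been fully adapted to this protocol.

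**Whether other text settles it.** The immune-mediated hepatitis paragraph in Section 7.1.1 sends the reader back to Section 6. The opening of Section 6 allows each drug to be modified independently when an event is clearly attributable to one of them, but it does not say which row governs nivolumab here. A general Grade 3 laboratory row in Table 4 prints a hold for nivolumab, but the ALT/AST rows are more specific.

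**Size.** Inputs: n = 36 (Section 11.1); Grade 3 ALT/AST rate p, not given, assumed 5% to 15%; fraction f of those cases meeting every footnote 5 condition, not given.

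Cases reaching the two rows, n x p:
- 36 x 0.05 = 1.8 and 36 x 0.15 = 5.4.
- Chance of at least one, 1 - (1 - p)^36: 1 - 0.95^36 = 0.84 and 1 - 0.85^36 = 0.997.

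Cases where the rows differ, n x p x f, with chance of at least one 1 - (1 - pf)^36:
- f = 25% (assumed): 0.45 to 1.35 patients; 1 - 0.9875^36 = 0.36 to 1 - 0.9625^36 = 0.75.
- f = 10% (assumed): 0.18 to 0.54 patients; 1 - 0.995^36 = 0.17 to 1 - 0.985^36 = 0.42.

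**Liver-test interval.** Footnote 5 sets tests every 3 days within its nivolumab-hold exception. Footnote 9, attached to the rucaparib entry, says "Monitor liver function tests weekly". Both apply only to a patient on nivolumab hold who continues rucaparib. Testing every 3 days also satisfies a weekly minimum, so the two can be met together, but the table does not say so.

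**The case against.** The strongest reply is that this is a stray cross-reference and little more. Both rows print discontinuation. Footnote 5 is worded for Grade 3 ALT or AST elevation in general, so a sensible reader could carry it over to the laboratory row and treat marker 7 as a mistake. The exception is narrow and already requires a discussion with the medical monitor. The primary endpoint definition, the sample size and the analysis are not touched.

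Much of this stands, and it limits the size of the point. It does not remove it. The laboratory row cites a different footnote, carries no relatedness limit and has an empty re-treatment cell. An investigator who follows it as printed is not directed to footnote 5, or to the discussion that footnote requires.

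Two stronger readings are tempting. A reader might infer that every Grade 3 ALT/AST case could keep or lose nivolumab depending on the row. The documents do not support that: for patients outside the footnote 5 conditions, these two rows give the same action. A reader might also infer that the two liver-test intervals contradict each other for any patient with Grade 3 ALT/AST who stays on rucaparib. They overlap only in the exception subgroup, where the shorter interval meets both.

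**Conclusion.** Table 4 is internally inconsistent on an operative treatment rule, and nothing else in the protocol resolves it. The conflict is confined to patients who meet all the footnote 5 conditions; elsewhere the two rows agree. The number affected cannot be derived from the documents. The range of 1.8 to 5.4 patients rests on an assumed 5% to 15% rate and counts everyone who reaches the two rows, so it is an upper bound. With an assumed 10% to 25% of them meeting the conditions, the expected number runs from 0.18 to 1.35.

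Marker 7 does not fit its row on any reading. The point should be corrected because the rule can decide whether a patient permanently loses a study drug. The liver-test interval is a secondary matter of clarity. No view is taken on which nivolumab action is right.

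**What to change.** In Table 4, reconcile the two Grade 3 ALT/AST rows so that they carry the same nivolumab action, the same relatedness qualifier and the same footnote. Replace marker 7 on the transaminase row. The sponsor decides which rule applies.

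As a secondary edit, state how the every-3-days test in footnote 5 and the weekly test in footnote 9 fit together for a patient on nivolumab hold who continues rucaparib.

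The cost is table and footnote wording in the next amendment. No new procedure, visit or data item is needed.
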